6.12.1 Patient Preparation – Valsalva Maneuver (VM)

The study subject will be trained in performance of the VM prior to conducting the SOC TCD (if performed) and NB-IS TCD bubble study in accordance with the training module developed by the principal investigators.

6.12.2 Contrast Agent Preparation

For TCD embolus detection, the contrast agent consisting of 9 mL bacteriostatic saline solution and 1 mL air should be mixed between two (2) 10-mL syringes connected by a 3-way stopcock at least ten (10) times and then vertically injected into (ideally) the right antecubital vein as a bolus both at Rest and mid-way through injection before a ten second Valsalva Maneuver (VM). The agitated saline should be mixed with 1 mL of blood prior to injection, if possible 14,15,16. If Definity

DWF-C0001-001 CONFIDENTIAL Page 24 of 44

(ultrasound contrast-agent containing perflutren lipid microspheres) is given during TTE or TEE prior to any TCD (NB-IS or SOC) *must* use different IV, wait up to 24h from Definity injection *and* record without injection (baseline recording) for 5 minutes prior to injecting air contrast (screen for Definity still circulating) before SOC TCD and NB-IS TCD bubble study sessions.

6.12.3 SOC Transcranial Doppler Ultrasound Procedure (TCD) (as applicable)

If SOC TCD bubble study is performed during subject participation in the study, preference is for this exam to be conducted in same session as the NB-IS TCD with the same individual administering the bubble injections with the SOC TCD bubble exam occurring before NB-IS TCD. The SOC TCD bubble study will be performed per standard of care, however, if possible, preference would be to collect measurements similar to NB-IS TCD exam (e.g., supine position at Rest and with VM, 45 degrees at Rest and with VM, etc.).

The following data points will be collected for the SOC TCD procedure:

- SOC transcranial Doppler Ultrasound (TCD) bubble study local results (SOC)
 - Date/time of SOC TCD bubble study
 - SOC TCD scan Start/Stop times with and without VM (as applicable)
 - Saline/Air Injection(s) Start/Stop time(s) with and without VM (as applicable)
 - Head inclination (degree)/subject positioning/location of the exam
 - Local Positive/Negative results for RLS/PFO
 - Local Spencer Logarithmic Scale (SLS) grade (with and without VM)
 - Local International Consensus Criteria (ICC) grade (with and without VM)

•

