6.5 Study Schedule

6.5.1 Schedule of Assessments

Schedule of Assessments					
Assessments	Screening ¹	Procedure ¹	Follow-Up ¹		
Informed Consent	х				
Demographics	Х				
Relevant Medical History	Х				
Physical Exam ◆	Х				
SOC TCD Bubble Study Exam ◆		O ⁴			
NB-IS TCD Bubble Study Exam		X ²			
Transthoracic Echocardiograph (TTE) Bubble Study ◆		X ³			
Transesophageal Echocardiograph (TEE) ◆		O ⁴ / X ⁸			
PFO Closure Decision ◆			X ⁵		
Classification of Potential Causative Mechanism in PFO–Associated Stroke ⁷ ♦			Х		
PFO Closure Procedure ◆			O _e		
Device-Related Adverse Events		Х			
Procedure-Related Adverse Events		х			
Concomitant Medications	х	х			
Device Deficiencies		Х			

- ♦ Standard of Care X = Required O = Optional, if performed
- 1. Screening, Procedure, and Follow-Up Visits can occur on the same day
- 2. NB-IS TCD performed with contrast agent of 9 ml bacteriostatic saline with 1 ml air mixed 10 times. Performed at Rest AND with VM 60 sec recordings each in supine positions AND with HOB raised to 45 degrees.
- 3. TTE can be performed within ±30 days of informed consent per SOC.
- 4. SOC TCD and TEE results collected if performed as applicable per standard of care.
- 5. PFO closure decision collected post diagnostic imaging procedures.
- 6. PFO closure procedure data collected within 60 days post diagnostic workup, if performed
- 8. SOC TTE or TEE will be required after the first 150 TTE subjects are enrolled and can be performed within ±30 days of informed consent per SOC.

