6.12.4 NeuralBot Investigational System (NB-IS) TCD Procedure

The NB-IS TCD bubble study session will be conducted beginning in the supine position with the same IV line.

The NB-IS TCD operator will setup the study subject in the headmount of the NeuralBot Investigational System as per Section 6.7 NeuralBot Investigational System Scanning Technique. When the signal search has completed and the optimal signal has been identified unilaterally or bilaterally, the NB-IS device will continue monitoring the signal(s) for up to 20 minutes during the delivery of the contrast agent at Rest and with VM.

First, 10 mL of mixed contrast agent will be injected into the right antecubital vein while the subject is at rest and the MCA signal recorded for a period of 60 seconds. The subject will remain at rest for approximately 3 to 5 minutes or when bubbles have cleared.

Second, another 10 mL of contrast agent will be injected in the right antecubital vein and the VM performed mid-way through injection, sustained for ten seconds. The MCA signal will be recorded for a period of 60 seconds; characteristic MCA waveform morphology change and mean velocity decrease of at least 25% will serve as proof of adequate Valsalva effort¹⁷.

This procedure will be repeated with the study subject in the reclined position, with head of bed raised to 45 degrees where 10 mL contrast agent is injected when the subject is at rest and subsequently with a Valsalva Maneuver.

DWF-C0001-001 CONFIDENTIAL Page 25 of 44

The following data points will be collected for the NB-IS TCD scanning session:

- Date/Time of NB-IS TCD bubble study
- NB-IS TCD Operator (name)
- NB-IS TCD Scan information
 - o NB-IS TCD scan Start/Stop times with and without VM
 - Saline/Air Injection(s) Start/Stop time(s) with and without VM
 - Head inclination (degree)/subject positioning/location of the exam
- Relevant Concomitant Medications
- Device-Related Adverse Events (NB-IS)
- Procedure-related adverse events related to agitated saline injection before and after VM (headache, allergic reactions, new onset neurological deficit, ischemic stroke, TIA or pulmonary embolism complicating agitated saline contrast injection, etc) will be closely monitored and prospectively collected¹⁸.
- Device Deficiencies / Malfunctions / Technical Observations

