11.2 Secondary Technical Efficacy Endpoint(s) Analysis

- % detection of false positives (FP), comparison of NB-IS TCD with TTE
- % detection of true negatives (TN) (specificity), comparison of NB-IS TCD with TTE
- % detection of false negatives (FN), comparison of NB-IS TCD with TTE
- Positive Predictive Value (PPV), comparison of NB-IS TCD with TTE
- Negative Predictive Value (NPV), comparison of NB-IS TCD with TTE
- Demonstration of NB-IS TCD diagnostic performance to SOC TCD for diagnostic accuracy parameters (sensitivity, specificity, PPV, NPV).
 - o If bilateral signals are found, the microbubble count will be sum across both vessels.
 - o If only a unilateral signal is found, the microbubble count will be doubled for the total count.
 - Spencer Logarithmic Scale (SLS) and International Consensus Criteria (ICC) gradings from the Imaging Core Lab for NB-IS TCD and SOC TCD will be compared for analysis.
- Demonstration of NB-IS TCD diagnostic performance targeting to transesophageal echocardiography (TEE) for diagnostic accuracy parameters (sensitivity, specificity, PPV, NPV).
- % detection of intervenable shunts, comparison of NB-IS TCD with TTE
 - For NB-IS TCD, Grade 3 and above (>30 microbubbles) on the Spencer Logarithmic Scale (SLS) and International Consensus Criteria (ICC) considered intervenable shunt¹⁰.
 - o For TTE, >20 microbubbles per 2016 American Society of Echocardiography Guidelines and Standards²³ considered intervenable shunt.
- NB-IS TCD No Window rate performance to SOC TCD parameters (including both unilateral and bilateral absent acoustic windows).
- % success rate of NB-IS TCD
 - o Incidence of failed registrations (device unable to register)
 - Incidence of bilateral signals not found (no evaluable signals found both sides)
 - Incidence of unilateral signals not found (evaluable signal found on one side)
 - An adequate, evaluable, and complete study is defined for the purposes of this protocol as successful acquisition of a unilateral signal at 40-65mm depth range recorded for the duration of the bubble study in the Resting position and with Valsalva Maneuver.
- Incidence of device malfunctions

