11.5 RLS/PFO Validation and Analysis

Evaluation of correlation between diagnostic imaging standard of care (SOC TCD/TTE/TEE) and NB-IS TCD diagnostic performance by an independent core laboratory. Success criteria will include clinical validation of NB-IS TCD for RLS/PFO detection targeting (i) 40% increase in NB-IS TCD sensitivity compared to TTE sensitivity and (ii) NB-IS TCD sensitivity ≥ 90% compared to SOC TCD sensitivity.

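### Robotic and manual TCD are compared without a rule for combining recordings or a matched-condition analysis, so the result can mix the device with the number and position of recordings

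*Combined protocol and SAP*

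**What the plan says.** **NB-IS TCD.** The schedule in section 6.5.1 marks the exam as required: "Performed at Rest AND with VM 60 sec recordings each in supine positions AND with HOB raised to 45 degrees". Section 6.12.4 describes rest and Valsalva injections in the supine position and then adds: "This procedure will be repeated with the study subject in the reclined position, with head of bed raised to 45 degrees". That makes four recordings. Sections 6.3 and 11.2, however, count a study as complete and evaluable once a one-sided signal is recorded at rest and with Valsalva. The 45-degree pair is not needed.

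**SOC TCD.** A footnote to the schedule makes it conditional: "SOC TCD and TEE results collected if performed as applicable per standard of care". Section 6.12.3 says "The SOC TCD bubble study will be performed per standard of care", and on similarity to the NB-IS exam goes no further than "if possible, preference would be to collect measurements similar to NB-IS TCD exam". It also prefers the same session and the same person injecting.

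**Comparison.** Section 11.2 plans sensitivity, specificity, PPV and NPV of NB-IS TCD against SOC TCD, and states that SLS and ICC "gradings from the Imaging Core Lab for NB-IS TCD and SOC TCD will be compared for analysis". Section 11.5 makes "NB-IS TCD sensitivity ≥ 90% compared to SOC TCD sensitivity" a success criterion. Section 11.2 does adjust for one-sided and two-sided signals, by doubling or summing counts. Neither section says which recordings count, how several become one call or grade, or that only conditions recorded with both devices are compared.

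**The concern.** Both exams yield the same kind of measurement, a microbubble count on TCD. If a subject's result is any-positive, the highest grade or the sum over recordings, the device with more recordings has more chances to find bubbles. Two identical devices would then differ.

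This matters because section 2.4 gives reduced user dependence of TCD as the rationale, and NB-IS against SOC TCD is the comparison closest to that question. It feeds criterion (ii), which sets no specificity requirement, so extra NB-IS positives can help it and cannot fail it. The cost would appear only in specificity and PPV against SOC TCD in section 11.2.

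**Working it through.** **1. The plan's own figure.** The only powered comparison is with TTE (section 11.6). With 100 × 0.30 = 30 subjects with a shunt, and discordant probabilities 0.45 and 0.05 (sum 0.50, difference 0.40), exact two-sided McNemar power is 0.89995, as tabulated. It says nothing about SOC TCD, for which the plan gives no sample size, interval or test.

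**2. Assumptions, none of them in the documents.** Identical devices; NB-IS with four recordings and SOC TCD with two; positive if any recording is positive; recordings exchangeable within a subject; subjects with a shunt only; two-recording detection 90%; latent-normal correlation ρ between recordings from 0 to 0.9; 30 SOC TCD positives.

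**3. Formulas.** Let N_k be the probability of no positive in k recordings, with the threshold set so that 1 − N_2 = 0.90.

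- Detection by four recordings: 1 − N_4.
- NB-IS positive given SOC positive, matched two against two: (1 − 2N_2 + N_4)/(1 − N_2).
- The same, unmatched four against two: (1 − N_2 − N_4 + N_6)/(1 − N_2).
- Chance of observing at least 90%: P(X ≥ 27), X binomial with n = 30 and that agreement.

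Hand check at ρ = 0: N_2 = 0.10, N_4 = 0.01, N_6 = 0.001. Matched: 0.81/0.90 = 90%. Unmatched: 0.891/0.90 = 99%.

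| ρ | Four detect | Agreement, matched | Agreement, unmatched | P(≥27/30), matched | P(≥27/30), unmatched |
|---|---|---|---|---|---|
| 0 | 99.0% | 90.0% | 99.0% | 65% | 99.98% |
| 0.3 | 97.3% | 91.9% | 98.2% | 78% | 99.8% |
| 0.5 | 96.0% | 93.3% | 98.1% | 86% | 99.7% |
| 0.7 | 94.6% | 94.9% | 98.2% | 94% | 99.8% |
| 0.9 | 92.6% | 97.1% | 98.8% | 99.0% | 99.95% |

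**4. Other calibration.** If two recordings detect 96.1%, the pooled TCD sensitivity in section 2.3, the matched chance is already 97% to 99.9% over the same range of ρ.

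**5. Other reading of criterion (ii).** If it means a ratio of sensitivities, identical devices give 1.00 when matched. Four against two gives 0.926/0.90 = 1.03 to 0.990/0.90 = 1.10. Extra recordings help NB-IS on both readings.

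**6. False positives.** Section 2.3 gives TCD specificity 92.4%, hence a 7.6% false-positive rate. Assuming this refers to two recordings, four give 1 − 0.924² = 14.6% at ρ = 0 and 9.8% at ρ = 0.9.

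**7. Grades.** If all six recordings in a subject are exchangeable, the highest count (ties aside) lies among the four NB-IS recordings with probability 4/6 = 67%, against 2/4 = 50% when matched. How many grades change depends on within-subject spread, which the documents do not give.

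**The case against.** **The mechanism needs a rule that the plan does not contain.** This stands. The shift arises under any-positive, highest or summed results. Section 6.12.3 collects local SOC grades with and without Valsalva, which would also fit condition-by-condition grading. The firm finding is therefore the missing rule; the shift follows only under some ways of filling it.

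**Four against two may not be typical.** This stands in part. A site that follows the preference in section 6.12.3 has matching sets and no imbalance. A subject with only the minimum evaluable NB-IS study has fewer than four recordings. The documents give no SOC TCD recording counts, so the frequency of imbalance is unknown.

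**The as-practised comparison is legitimate.** This stands. Section 4 sets the aim relative to standard-of-care techniques, and NB-IS against SOC TCD as performed locally answers that. It cannot separate the robot from the recording set, so a matched analysis belongs beside it, not in its place.

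**Core-lab reading protects the comparison.** Only partly. Blinded central reading under section 11.4 addresses reader differences, not unequal numbers of recordings.

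**Conclusion.** The plan leaves open how recordings become a subject-level call or grade, and has no analysis limited to conditions recorded with both devices. The comparison can therefore credit NB-IS for extra recordings.

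Under the stated assumptions, positive agreement rises from 90–97% matched to 98–99% unmatched. The effect on passing criterion (ii) ranges from large (65% to above 99% at correlation 0) to negligible (99.0% to 99.95% at 0.9), and it nearly vanishes if two recordings detect 96.1%.

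Two stronger readings are tempting. One is that criterion (ii) is bound to be met through extra recordings. The documents do not support it: they state no combining rule and no SOC recording counts, the largest jump needs recordings in the same person to be independent, and matched agreement for identical devices is already at or above 90% throughout the table. The other is that the as-practised comparison is wrong; given the objective in section 4, it is not. This is a worthwhile improvement to the plan, not a fatal flaw.

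**What to change.** In sections 11.2 and 11.5:

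1. State one rule, the same for both devices, for turning recordings into a subject-level call and SLS/ICC grade; for example, positive if any, and highest grade, over the conditions included.
2. Prespecify a matched NB-IS versus SOC TCD analysis limited to conditions (head position and rest/Valsalva state) recorded with both devices in the same subject, read by the core lab.
3. Report it beside the all-recordings, as-practised comparison, with the number of recordings per device.
4. Claim equivalence of robotic and manual acquisition, including through criterion (ii), only if the matched result also meets the target.
5. If recordings are also paired one by one, account for clustering within subject.

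**Cost.** A few sentences in the plan and a matched analysis file; no new procedure, visit or subject. Head inclination and scan times with and without Valsalva are collected for both devices (sections 6.12.3 and 6.12.4). SOC times are collected only as applicable, and inclination is listed once per exam, so confirm that both can be tied to each recording and that the core lab keeps its reads by recording. NB-IS recordings without an SOC TCD counterpart drop out of the matched analysis only, where NB-IS figures may be less favourable. The TTE and TEE comparisons are untouched.

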6.12.4 NeuralBot Investigational System (NB-IS) TCD Procedure

The NB-IS TCD bubble study session will be conducted beginning in the supine position with the same IV line.

The NB-IS TCD operator will setup the study subject in the headmount of the NeuralBot Investigational System as per Section 6.7 NeuralBot Investigational System Scanning Technique. When the signal search has completed and the optimal signal has been identified unilaterally or bilaterally, the NB-IS device will continue monitoring the signal(s) for up to 20 minutes during the delivery of the contrast agent at Rest and with VM.

First, 10 mL of mixed contrast agent will be injected into the right antecubital vein while the subject is at rest and the MCA signal recorded for a period of 60 seconds. The subject will remain at rest for approximately 3 to 5 minutes or when bubbles have cleared.

Second, another 10 mL of contrast agent will be injected in the right antecubital vein and the VM performed mid-way through injection, sustained for ten seconds. The MCA signal will be recorded for a period of 60 seconds; characteristic MCA waveform morphology change and mean velocity decrease of at least 25% will serve as proof of adequate Valsalva effort¹⁷.

This procedure will be repeated with the study subject in the reclined position, with head of bed raised to 45 degrees where 10 mL contrast agent is injected when the subject is at rest and subsequently with a Valsalva Maneuver.

DWF-C0001-001 CONFIDENTIAL Page 25 of 44

The following data points will be collected for the NB-IS TCD scanning session:

- Date/Time of NB-IS TCD bubble study
- NB-IS TCD Operator (name)
- NB-IS TCD Scan information
 - o NB-IS TCD scan Start/Stop times with and without VM
 - Saline/Air Injection(s) Start/Stop time(s) with and without VM
 - Head inclination (degree)/subject positioning/location of the exam
- Relevant Concomitant Medications
- Device-Related Adverse Events (NB-IS)
- Procedure-related adverse events related to agitated saline injection before and after VM (headache, allergic reactions, new onset neurological deficit, ischemic stroke, TIA or pulmonary embolism complicating agitated saline contrast injection, etc) will be closely monitored and prospectively collected¹⁸.
- Device Deficiencies / Malfunctions / Technical Observations

6.12.5 Transthoracic Echocardiography Procedure (TTE) per SOC

The TTE bubble study can be performed per standard of care within ±30 days of informed consent.

The following data points will be collected for the TTE procedure:

- Transthoracic Echocardiography (TTE) local results (SOC)
 - Date/Time of TTE bubble study
 - TTE Start/stop times with and without VM (as applicable)
 - Saline/Air Injection(s) Start/Stop time(s) with and without VM (as applicable)
 - Local Positive/Negative results for RLS/PFO
 - Local Bubble Count (as applicable)
 - Local TTE grading (as applicable)

6.12.6 Transesophageal Echocardiography Procedure (TEE) per SOC (as applicable)

The study subject, if referred per the institution's standard practice, will then undergo scheduled transesophageal echocardiography (TEE) bubble study with and without VM similarly to NB-IS TCD procedure.

The following data points will be collected for the TEE procedure, if performed:

- Transesophageal Echocardiography (TEE) local results (SOC) including shunt size and presence of atrial septal aneurysm.
 - Date/Time of TEE exam
 - TEE Start/Stop times with and without VM (as applicable)
 - Saline/Air Injection(s) Start/Stop time(s) with and without VM (as applicable)
 - Local Positive/Negative results for RLS/PFO
 - Local Bubble Count (as applicable)
 - Local TEE grading (as applicable)

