2.3 Limitations

Although TTE is the most frequently used non-invasive technique for the assessment of RLS, it is limited by its dependence on the expertise of the technician performing the exam. Furthermore, its moderate sensitivity (45.1%) but high specificity (99.6%) in RLS indication should not be relied upon in the determination of treatment for ESUS patients⁶.

While TEE is considered the gold standard for visualization of the PFO after its presence has been indicated, its invasive nature can make it difficult for the patient to comply with the necessary steps for the VM. Although TEE is contraindicated in patients with dysphagia or esophageal issues, its sensitivity and specificity are 95% and 95% for indication of RLS⁷.

Like TTE, the diagnostic value of TCD is limited by the expertise of the technician performing the exam and the presence of optimal acoustic windows. Signal acquisition is a well-documented obstacle in TCD evaluation regardless of pathology and is no different in the case of RLS

DWF-C0001-001 CONFIDENTIAL Page 14 of 44

assessment⁸. However, unlike TTE, TCD has shown excellent sensitivity and specificity in RLS detection (96.1% and 92.4%, respectively) against the gold standard of TEE⁶.

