2.5 Potential Risks and Benefits

TCD ultrasonography is a safe, non-invasive, and reproducible technique that allows the assessment of cerebral blood flow (CBF) in a person. TCD data collection relies on the level of experience of a TCD technologist to acquire an accurate and high-quality signal from the intracranial vessel(s) of interest, thus per user, the data quality is variable⁹. NovaSignal has developed the NeuralBot Investigational System (NB-IS) to assist in the TCD data collection such that consistent high-quality data may be obtained independent of the experience of the user.

NovaSignal will collect safety and technical feasibility data regarding the use of TCD ultrasound via the NeuralBot Investigational System (NB-IS) device in humans. Data collected during this study is for research purposes only. No treatment or healthcare decisions will be made based on study measurements collected in this study.

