5.4.1 Inclusion Criteria

A subject must meet all of the following inclusions criteria to be enrolled in the study:

- 1. Subject 18 years of age and older.
- 2. Subject presents with a clinical condition characterized by neurological signs and symptoms that, in the opinion of the investigator, include embolic stroke or TIA in the differential diagnosis.
- 3. Scheduled for a transthoracic echocardiograph (TTE) or transesophageal echocardiograph (TEE) study with agitated saline contrast (bubble study) within ±30 days of informed consent.
- 4. Subject is able to successfully perform a Valsalva Maneuver (VM).
- 5. Subject or Legally Authorized Representative has the ability to provide informed consent and comply with the protocol.

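### NB-IS accuracy against TEE is estimated only in subjects sent to TEE in routine care; the plan neither adjusts for that selection nor limits the conclusion to those subjects

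*Combined protocol and SAP*

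**What the plan says.** No section requires TEE in every subject or in a random sample. Section 6.12.6 has it done "if referred per the institution's standard practice". Note 4 to the schedule in Section 6.5.1 reads "SOC TCD and TEE results collected if performed as applicable per standard of care". In the sub-study either test is enough: note 8 says "SOC TTE or TEE will be required after the first 150 TTE subjects are enrolled", and Section 5.4.1 admits a subject who is "Scheduled for a transthoracic echocardiograph (TTE) or transesophageal echocardiograph (TEE) study with agitated saline contrast".

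On how patients reach TEE, Section 2.2 treats TTE and TCD as the initial imaging and TEE as the later assessment. Section 2.3 calls TEE the "gold standard for visualization of the PFO after its presence has been indicated". On the role of the study device, Section 2.5 states "No treatment or healthcare decisions will be made based on study measurements collected in this study".

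Section 11.2 lists as a secondary analysis "Demonstration of NB-IS TCD diagnostic performance targeting to transesophageal echocardiography (TEE) for diagnostic accuracy parameters", namely sensitivity, specificity, PPV and NPV. Section 11 contains no adjustment for incomplete verification, no sensitivity analysis and no description of subjects without TEE. Section 11.6 gives 147 patients for a 95% interval 20 points wide around a sensitivity of 90% against TEE, at 30% prevalence.

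**The concern.** If TEE usually follows a positive first test, the subjects with a TEE result are not a fair sample of those enrolled. Shunts seen on TTE or SOC TCD are over-represented. Large shunts are easier to see on any bubble test, so NB-IS probably does better in these subjects than in shunts the other tests missed. Crude sensitivity would then be too high and crude specificity too low. Enriching the verified group with shunts also changes PPV and NPV, whatever happens to the other two measures.

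TEE is the reference against which the protocol itself quotes TCD accuracy (Section 2.3). A reader will therefore take the TEE results as the device's accuracy in patients with suspected embolic stroke or TIA. The plan does not say that they describe a referred subset.

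**Working it through.** **Plan figures reproduced.** With an exact (Clopper-Pearson) 95% interval, the smallest number of shunt-positive subjects giving a width of at most 0.20 at 90% is 44 (width 0.198). 44 / 0.30 = 146.7, which gives the stated 147. An exact two-sided McNemar test with 30 shunt-positive subjects out of 100, discordance D = 0.50 and difference 0.40 has power 0.89995, as tabulated in Section 11.6. So D is the discordant proportion among shunt-positive subjects.

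**Inputs.** From Section 11.6: sensitivity 0.90 (TCD) and 0.50 (TTE), D = 0.50, prevalence 0.30. From Section 2.3: TCD specificity 0.924, TTE specificity 0.996. Assumed, because the documents give none: TEE in 80% of TTE-positives and 20% of TTE-negatives. TEE is treated as the truth.

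**Sensitivity.** Among shunt-positive subjects, NB-IS+/TTE− = (D + 0.40)/2 and NB-IS+/TTE+ = 0.90 − (D + 0.40)/2. Observed sensitivity = [0.8 × (NB-IS+/TTE+) + 0.2 × (NB-IS+/TTE−)] / (0.8 × 0.5 + 0.2 × 0.5), with denominator 0.50.

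| D | NB-IS+/TTE+ | NB-IS+/TTE− | Observed sensitivity |
|---|---|---|---|
| 0.50 | 0.450 | 0.450 | 0.450/0.50 = 90% |
| 0.45 | 0.475 | 0.425 | 0.465/0.50 = 93% |
| 0.40 | 0.500 | 0.400 | 0.480/0.50 = 96% |

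At D = 0.50 the both-positive cell is 0.45 = 0.90 × 0.50. The tests are then independent given a shunt, and TTE-driven referral causes no bias at any referral rates. D = 0.40 is the minimum for a 40-point difference: every TTE-positive shunt is also NB-IS-positive. Over assumed TTE+/TTE− referral from 100/50% to 80/10%, the range is 91.7% to 93.9% at D = 0.45 and 93.3% to 97.8% at D = 0.40.

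**Specificity.** With maximal dependence among shunt-negative subjects and 80/20 referral: 0.924 × 0.2 / (0.004 × 0.8 + 0.996 × 0.2) = 0.1848/0.2024 = 91.3%, against 92.4%. Over the wider referral range it is 92.0% down to 89.9%.

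**Referral on SOC TCD, upper bound.** If SOC TCD tracked NB-IS perfectly, sensitivity would be 0.90/(0.90 + 0.10 × 0.5) = 94.7% at 100/50% referral and 0.72/(0.72 + 0.01) = 98.6% at 80/10%. Specificity would be 0.462/(0.462 + 0.076) = 85.9% and 0.0924/(0.0924 + 0.0608) = 60.3%.

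**PPV and NPV at D = 0.50, 80/20 referral.** Verified with shunt: 0.30 × (0.5 × 0.8 + 0.5 × 0.2) = 0.150. Verified without: 0.70 × (0.004 × 0.8 + 0.996 × 0.2) = 0.142. Prevalence among verified = 0.150/0.292 = 51%. The table holds sensitivity at 0.90 and specificity at 0.924, so it also assumes independence among shunt-negative subjects.

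| | Enrolled (30%) | Verified (51.4%) |
|---|---|---|
| PPV | 0.270/(0.270 + 0.0532) = 84% | 0.463/(0.463 + 0.0369) = 93% |
| NPV | 0.6468/(0.6468 + 0.030) = 96% | 0.449/(0.449 + 0.0514) = 90% |

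**Can it be adjusted?** In a worked case with D = 0.40 and 80/30% referral, crude sensitivity and specificity are 94.5% and 91.8%. A Begg-Greenes estimate stratified by NB-IS × TTE returns 90.0% and 92.4%. Stratifying by NB-IS alone leaves sensitivity at 90.6%, so TTE has to be in the strata.

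**The case against.** A reader might infer that sensitivity and specificity are certainly biased. The documents do not support that. NB-IS results do not enter care, so the direct form of verification bias is absent. Under the plan's own D = 0.50 with TTE-driven referral, the sensitivity bias is zero. The 96% needs the boundary value of D. Sections 2.2 and 2.3 make referral after a positive first test plausible, but no section states the drivers or the rates. This stands, and it is why the point is one of risk. It does not rescue PPV and NPV. Moreover, D = 0.50 is a sample-size input and not evidence that the tests are independent.

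A reader might also infer that the data for a full adjustment are already collected. Only partly. NB-IS and TTE are both required in the main study. SOC TCD is recorded only if performed, the listed data items do not include the reason for TEE referral, and Section 6.3 removes all data from subjects with inadequate scans. Sub-study subjects who enter on a scheduled TEE may have no TTE and have no unverified counterparts. That is selection before enrolment, which reweighting cannot repair.

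Finally, TEE accuracy is one secondary endpoint, listed as percent agreement in Section 4.2, with a planned interval 20 points wide; a 3-point bias at D = 0.45 is small beside it. Nor is TEE an error-free reference: Section 2.3 quotes it at 95% and 95%. These are fair limits on importance. But a systematic shift does not shrink with sample size, and a wide interval does not show it.

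**Conclusion.** The TEE comparison is at risk of verification and selection bias, and the plan neither handles it nor narrows the claim. At assumed 80/20 TTE-driven referral, crude sensitivity lies between 90% (no bias, D = 0.50) and 96% (boundary, D = 0.40) for a true 90%. Specificity moves by about one point at most, from 92.4% to 91.3%. Larger shifts need referral on a SOC TCD that agrees closely with NB-IS. The firmest part is that crude PPV and NPV would misdescribe the enrolled population even with unbiased sensitivity: about 93% against 84%, and 90% against 96%. All sizes depend on assumed referral rates and on TEE as truth.

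It would be wrong to infer that the trial's success is in question. Both success criteria in Section 11.5 compare NB-IS with TTE and SOC TCD, and neither uses the TEE result.

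**What to change.** Amend Section 11.2 as follows:

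1. Label the crude TEE results as *among subjects with clinically indicated TEE*, and do not present PPV or NPV as applying to the enrolled population.
2. For evaluable main-study subjects, pre-specify a supportive Begg-Greenes or inverse-probability-of-verification estimate stratified by NB-IS × TTE, adding SOC TCD only where performed. Report its interval and the number verified in each cell.
3. Report subjects who entered the sub-study on a scheduled TEE separately.
4. Tabulate subjects with and without TEE side by side: demographics, medical history, and NB-IS and TTE results.

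The cost is analysis time; no procedure or visit is added. The adjusted estimate assumes that referral is explained by the recorded results. It also rests on few verified TTE-negative shunts: 150 × 0.30 × 0.50 × 0.20 = 4.5 at 20% referral, or about 2 at 10%. These few represent half of all shunts, so the interval will be wide and a bootstrap may be unstable. The estimate should therefore stand beside the crude figures as supportive only.
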